
### **Exempt and Expedited**

**Is the purpose of this submission to obtain an exemption determination, in accordance with 45CFR46.101(b):**  
No

---

**Is the purpose of this submission to seek expedited review , as per the federal categories referenced in 45CFR46.110?**

No

### **Funding**

**Is there any external funding or support that is applied for or awarded, or are you the recipient of a gift, for this project?**

Yes

| Award Type   | Funding Source Name | Name of awarding agency                             | Status           | Award # or Application Date | Federal/State /Local Government Direct or Subcontract | What is the award covering? | Rascal PT Number |
|--|---------------------|---|------------------|-----------------------------|---|-----------------------------|------------------|
| Federal/State/ Local Government  | NIH                 | National Heart, Lung, and Blood Institute/NIH/ DHHS | Awarded/Received | R01HL128226                 | Direct Recipient: With Subcontract Sites              | Entire Protocol             | PT-AABL8020      |
| Subcontract site(s), procedures taking place at each site and FWA# for federally funded studies:
NYULMC performs fMRI measurements; University of Manitoba is analyzing doubly-labeled water samples |                     |   |                  |                             |   |                             |                  |

## Privacy & Data Security

**Indicate the methods by which data/research records will be maintained or stored (select all that apply):**

Hardcopy (i.e., paper)

**Describe where and how the data will be stored:**

All files with participant identifying information will be kept in a locked file cabinet in the PI's office

Electronic

**Where will the data be stored?**

Y

On a System

On an Endpoint

**Identify what type of endpoint will be used (select all that apply):**

Desktop Computer

Laptop Computer

Mobile Device

Other

**Does this study involve the receipt or collection of Sensitive Data?**

Yes

**If any Sensitive Data is lost or stolen as part of your research protocol, you must inform both the IRB and the appropriate IT Security Office (CUMC IT Security if at CUMC; CUIT if at any other University campus).**

**What type of Sensitive Data will be obtained or collected? Select all that apply:**

Personally Identifiable Information (PII), including Social Security Numbers (SSN)

**Will Social Security Numbers (SSNs) be collected for any purpose?**

Yes

**Describe the purpose for collection of SSNs:**

subject payment

**Describe the plan to protect SSN confidentiality:**

w-9 forms will not be stored with subject data

**Will SSNs be disclosed outside of Columbia for any purpose?**

No

Protected Health Information (PHI), including a Limited Data Set (LDS)

**If any PHI is lost or stolen, you must inform both the IRB and the Office of HIPAA Compliance.**

**Indicate plans for secure storage of electronic sensitive data: check all that apply**

Sensitive data will not be stored in electronic format

Sensitive data will be stored on a multi-user system

Sensitive data will be stored on an encrypted endpoint

**By Selecting an Endpoint Device and approving this protocol for submission to the IRB, the PI is attesting that the device and any removable media that may be used have been or will be registered and/or will be maintained in compliance with the University's Information Security Charter and all related policies. It is important that this information is updated, during the course of the study, as new devices are added.**

---

**Provide a description of how the confidentiality of study data will be ensured, addressing concerns or protections that specifically relate to the data storage elements identified above (e.g. hard copy, electronic, system, and/or endpoint):**

Data files will be password protected and exchanged in secured servers. Only individuals involved in the study conduct will have access to those files and HIPAA regulations will be followed. All data transmitted among investigators will be coded and shared via encrypted devices. Data obtained via mobile devices (e.g., tablets) will not contain PII/PHI, and will be transferred to secure endpoints via the CUMC athens wireless network, or otherwise via a physical connection (e.g. USB, microSD).

**If your project is not NIH funded, has a Certificate of Confidentiality (CoC) been requested for this research?**

No

**Provide a description of the protections in place to safeguard participants' privacy while information is being collected:**

Data files will be password protected and exchanged in secured servers. Only individuals involved in the study conduct will have access to those files and HIPAA regulations will be followed. All data transmitted among investigators will be coded and shared via encrypted devices. Data obtained via mobile devices (e.g., tablets) will not contain PII/PHI, and will be transferred to secure endpoints via the CUMC athens wireless network, or otherwise via a physical connection (e.g. USB, microSD).

## Procedures

**Is this project a clinical trial?**

Yes

**Is this project a clinical trial that requires registration with [www.clinicaltrials.gov](http://www.clinicaltrials.gov)?**

Yes

**Has this study been registered with [www.clinicaltrials.gov](http://www.clinicaltrials.gov)?**

Yes

**Please provide the registration number:**

NCT02960776

**Is this project associated with, or an extension of, an existing Rascal protocol?**

No

**Do study procedures involve any of the following?**

**Analysis of existing data and/or prospective record review**

No

**Audio, video or photographic recording of research subjects**

No

**Behavioral Intervention?**

Yes

**Biological specimens (collection or use of)**

Yes

**Cancer-related research**

No

**Drugs or Biologics**

No

**Future use of data and/or specimens**

Yes

**Genetic research**

No

**Home Visits**

No

**Human Embryonic and/or Human Pluripotent Stem Cells**

No

**Imaging procedures or radiation**

Yes

**Medical Devices**

Yes

**Surgical procedures that would not otherwise be conducted or are beyond standard of care**

No

**Will any of the following qualitative research methods be used?**

**Survey/interview/questionnaire**

Yes

**NOTE: You must attach a PDF version of the survey(s)/interview(s)/questionnaire(s) to this protocol prior to submission.**

**Systematic observation of public or group behavior**

No

**Program evaluation**

No

**Will any of the following tests or evaluations be used?**

**Cognitive testing**

Yes

**Educational testing**

No

**Non-invasive physical measurements**

Yes

**Taste testing**

No

**Is there a stand-alone protocol that describes ALL procedures in this study?**

No

**Please describe ALL study procedures in detail.**

**NOTE: Be sure to detail all of the procedures above to which a "yes" response was selected. Also detail any additional procedures that may or may not fall into the categories listed above.**

**Overview of Procedures**

We propose a randomized, crossover, outpatient sleep restriction study with 2 phases of 6 wk each. The sleep durations will be the participant's regular bed- and wake-times during the HS phase and HS minus 1.5 h in the SR

phase. During the HS phase, participants will be asked to follow a fixed bedtime routine based on their screening sleep schedule. During the SR phase, participants will be asked to keep their habitual wake time constant but delay their bedtime to achieve a reduction of 1.5 h in total sleep time. A delay in bedtimes was chosen rather than advancing wakeup time because it most closely reflects differences in sleep timing behavior between short and habitual sleepers. In fact, the longer sleep duration of individuals in the Central time zone compared to that of those in Eastern or Pacific time zones [58] is hypothesized in part to be due to late night shows being broadcast one hour earlier in the Central time zone [59]. Individuals in Eastern or Pacific time zones stay up later at night to watch those shows. Adolescent short sleepers have later bedtimes than normal sleepers [60]. Moreover, delaying bedtimes increases exposure to light at night which is associated with weight gain and obesity [61]. Providing individualized bedtimes and wakeup times for each participant was chosen to ensure that participants are not phase-shifting their sleep episode for the purpose of this study. Two weeks prior to randomization and during washout periods, participants will wear an actigraph (ActiGraph wGT3X-BT activity monitor, Pensacola, FL) and keep a sleep diary to verify sleep duration and sleep-wake schedule. In addition to achieving an average sleep of 7-9 h/night, per wrist actigraphy, participants will only be enrolled if they achieve 7 h of sleep for at least 10 of the 14 nights of screening and have <4 nights with <6 h of sleep. We have successfully used this screening protocol in several studies [8, 28]. The actigraph monitors will be provided by the research team. At randomization, a urine pregnancy test (for women) and drug screen will be performed. Participants will be asked to abstain from caffeine and alcohol intake for 24 h prior to the start of each study phase. Between study phases, if participants have not returned to baseline sleep patterns, an additional 2-4 wk washout period will be provided. In general, washout periods will be 6 wk in duration. This washout length enhances the likelihood that women will be in the same phase of their menstrual cycle at the start of each experimental phase. On the first day of each study phase (baseline), participants will come to Irving Center for Clinical and Translational Research (CTSA) at Columbia University in the morning after an overnight, 12-h fast. Participants will have anthropometric and blood pressure measurements taken, will provide a fasting blood sample, undergo performance/vigilance testing, and will then be taken to the department of Radiology to undergo MRI scanning to assess body composition. Participants will begin the fixed bedtime routine that night. These baseline measurements will be repeated at endpoint, 6 wk later. Body weight, waist circumference, and blood pressure will be measured weekly, fasting blood and urine samples will be taken at baseline, week-3, week-4, and endpoint, during adherence check visits. A non-fasting blood sample will be taken at week-5 adherence check visits. During the last week of each phase, 1 h before the participant's self-reported usual dinner time they will be escorted to NYU for an fMRI. They will fill out a visual analog scale and the Stanford Sleepiness Scale, before and after the scan. During the last week of each phase, participants will undergo performance testing (6-minute walking test).

#### Ensuring adherence to the sleep protocol.

Participants will be blinded to the purpose of the study to ensure that they do not alter their habits by knowing the hypothesis that SR may cause weight gain. Participants will be told that the purpose of the study is to assess the effects of mild SR on mood and cognitive and physical performance. Questionnaires and physical performance tests will be administered at baseline and bi-weekly, to maintain blinding. We also have a well-defined strategy for ensuring adherence to the sleep protocol in this outpatient setting. Participants will be given written instructions on study procedures and investigator phone calls will be made as reminders of the bedtimes and wakeup times on a weekly basis. To verify that participants adhere to the sleep protocol, they will be asked to keep a sleep diary and wear an activity monitor 24 h/d. Participants will wear an actigraphy monitor on their wrist (ActiGraph wGT3X-BT activity monitor, Pensacola, FL), which will serve to track their sleep duration, sleep timing, and ambient light. This watch is water resistant and therefore does not need to be removed to shower or swim. To further ensure compliance with the sleep protocol, participants will be required to come to the research center on a weekly basis. This weekly visit will serve several purposes: (1) download data from the Actiwatch (verify sleep duration); (2) charge the watch; (3) obtain weekly diaries (verify bedtimes and wakeup times) and other questionnaires; (4) obtain body weight measurement and blood and urine samples. Participants will be told a priori, as part of the screening process, that they must adhere to the sleep protocol to continue to participate in the study and that adherence will be checked weekly. Non-adherent

participants will be terminated from the study. Adherence will be defined as having bedtimes and wake times within 30 min of scheduled times at least 5 d/wk and achieving an average of >7 h of sleep each week with no more than one night/wk of sleep <7 h during the HS phase and achieving an average sleep reduction of 1.5 h from screening sleep duration each week with no more than one night/wk with <1.5 h of restriction during the SR phase. Daytime naps will not be permitted. Participants will receive weekly incentives, in the form of a gift card, for their continued adherence to the sleep protocol.

#### Detailed methods for outcome variables

##### Body composition measurements.

Anthropometric measurements will be obtained at the NYORC Human Phenotyping/Body Composition Core Laboratory ([name], Ed.D. Core laboratory Director). A single trained technician will obtain all measurements for this study using laboratory standard procedures. Height, weight, and body circumferences (waist and hip) will be measured in duplicate with the participant wearing only a hospital gown and no shoes. The Body Composition Laboratory is a world-renowned center for the measurement of body composition and has been involved in cutting-edge research for the development of new body composition assessment techniques, estimation equations, and validation of new measurement tools.

Body composition will be measured by MRI at baseline and endpoint. Briefly, a full body scan will be done using a 1.5T GE MRI (GE Healthcare) in the Department of Radiology at Columbia University Medical Center. We acquire 10 mm thick slices at 40 mm intervals throughout the body. All body compartments will be segmented at the New York Image Analysis Laboratory ([name], Core laboratory Director) by trained technicians, who regularly undergo quality control and cross-validation, using SliceOmatic image analysis software (Tomovision, Montreal, Canada). Technicians will be blinded to sleep study phase assignment and test dates. This protocol will allow us to quantify muscle mass, organ mass, and subcutaneous, visceral, and intermuscular adipose tissues for the whole body and for left and right sides and upper and lower body. MRI provides images of the entire visceral area, a major advantage over other imaging techniques. Another advantage of this methodology is the lack of radiation exposure and whole-body measurements of visceral and subcutaneous adipose tissues. As MRI scanning is very safe, repeated measurements can be performed frequently on the same individual. In this study, we chose to perform a whole-body scan rather than the common single-slice imaging as we have shown that multi-slice imaging was better and more cost-effective at detecting changes in visceral and subcutaneous adipose tissue than a single slice. In the present study, participant costs are higher than imaging costs. Therefore choosing a more precise body composition assessment method that reduces the need for additional participants represents a cost-saving option.

##### Energy expenditure.

EE will be assessed using doubly labeled water (DLW), during the last 2 wk of each sleep phase. At the 4-wk compliance check, participants will be asked to provide a urine and a saliva sample prior to taking a dose of DLW (1.6 - 2.5 g O, 10% atom percentage excess [APE] and 0.12 g H2O 99.9% APE per kg estimated body water). This will be followed by a 50 mL water rinse. Participants will be asked to minimize food and beverage consumption over the following 4 h and to collect saliva samples at 3 and 4 h post-dosage. Participants will be given vials to collect these samples as well as cups to collect second void urine samples at 24 h, 7 d, and 14 d post-dosing. Participants will be asked to freeze their samples at home and bring them to the research center at the next compliance check visit. Isotope measurements will be made by Off-Axis Integrated Cavity Output Spectroscopy in the laboratory of [name] (Anschutz Medical Campus, University of Colorado, CO). These measurements will be obtained in younger adults only.

We will also assess physical activity level by waist actigraphy (GT3X Actigraph LLC, Pensacola, FL) throughout each study phase. We hypothesize that total EE and physical activity level will be lower during the period of SR compared to

HS.

Resting-state and food-viewing stimulated neural activity.

Brain responses will be assessed using two fMRI paradigms (resting state and task-based) at wk 6, 1 h before the participant's self-reported usual dinner time. The resting state paradigm and intrinsic functional connectivity (iFC) analysis will assess treatment effects on reward and interoception-related neuronal circuitry. During the resting state scan (2 runs, each ~ 5 mins), participants will focus on the fixation cross in the center of the screen. Wakefulness and compliance with eyes-open instructions will be monitored via an eye-tracking camera and verbal reminders given before every run. Pulse and respiration rates will be measured using MRIcompatible non-invasive physiological monitoring equipment. Recent data by Fang et al. [71] reported altered resting state striatal connectivity after a night of total sleep deprivation, which was correlated with increases in EI. We will explore whether this is the case in the proposed conditions. The task-based paradigm has been validated in several studies, including our Sleep Study. The 2-by-2 block design protocol includes 4 runs (~3 min each) each consisting of 4 blocks (2 foods and 2 non-foods) during which participants view 5 items presented for 4 s each (total=20 s) using E-Prime 2 (Psychology Software Tools, Inc., Pittsburgh, PA). Each block is separated by a 20 s basal period during which participants view a fixation cross. [The order of blocks in a run is constant for each participant with the specific stimuli that the individual ranked highest in a preference rating questionnaire prior to scanning. Our pilot R56 grant data (R56 HL119945) suggested a relatively uniformly distributed range of preferences across the initial 40 food and 40 non-food items that each participant ranked. This preliminary finding supports the feasibility of including images that are rated as "mildly appealing" up to "very appealing".] Importantly, in our previous Sleep Study, scanning was performed in the fasted state in the morning. Since it has been proposed that SR induces greater evening intakes specifically, we chose to perform our measurement approximately 1 h prior to the participant's usual dinner, a time when individuals may be most susceptible to be hyper-responsive to food stimuli in SR relative to HS, thus increasing sensitivity for capturing the effect of SR.

Imaging parameters.

fMRI scanning will take place at the NYULMC Center for Biomedical Imaging using [the same Siemens 3T Skyra scanner (Siemens USA, Malvern, PA) used in our R56 pilot study.] Head motion will be minimized by placing restraint pads around the head. A T1-weighted anatomical image [(MPRAGE sequence: TR=1900 ms; TE=2.52 ms; TI=900 ms; flip angle=9°; 176 slices, FOV=250 mm, voxel size=1x1x1 mm) will be acquired for image co-registration and spatial localization. For both resting-state and task-based paradigms, functional data will be acquired using a single-shot gradient echo planar imaging (EPI) T2\*-weighted sequence (TR=2500 ms; TE=30 ms; Flip angle=80°, 38 slices, matrix=64x64; FOV=216 mm; voxel size=3x3x3 mm).] To examine structural connectivity, we will acquire diffusion-weighted data using an echo-planar sequence (TR=5.2 s, TE=78 ms, 32 directions, b=1000 s/mm^2; acquisition voxel size=2x2x2 mm).

Image analysis.

Image processing will be carried out using [FMRIB Software Library (FSL, [www.fmrib.ox.ac.uk](http://www.fmrib.ox.ac.uk)) and Configurable Pipeline for the Analysis of Connectomes (C-PAC, <http://fcpindi.github.com>).] Preprocessing will comprise (1) slice time correction, (2) 3-D motion correction, (3) spatial smoothing (FWHM=6 mm), (4) mean-based intensity normalization, (5) temporal band-pass filtering (restingstate data only; 0.009-0.1 Hz), and (6) linear and quadratic detrending. Linear registration of each participant's functional time series to their high-resolution structural image and non-linear registration of high-resolution structural images to the Montreal Neurological Institute (MNI) template with 2 mm resolution will be performed using FLIRT and FNIRT [73, 74]. [Given that head motion in 100% of our preliminary task-related and resting state data was much lower than field standards (mean head motion for each of the 4 task and 2 rest functional runs ranging between 0.073 mm and 0.078 mm, substantially lower than the field standard of 0.2 mm), we anticipate implementing 'scrubbing' to salvage offending segments with excessive motion, if necessary. Task:

Neural responses during food and non-food blocks will be assessed using a box-car convolved with a hemodynamic response function (HRF) as implemented in FEAT [78]. A direct contrast of food relative to non-food blocks will identify brain regions sensitive to food processing. Group-level random-effects analyses will compare neural activation for food>nonfood stimuli using paired t-test between HS and SR. Whole-brain correction for multiple comparisons will be performed ( $Z>2.3$ ; cluster significance:  $p<0.05$ , corrected). Finally, we will use resting state and task-based data to assess activity of the DMN (regions of the posterior cingulate gyrus, medial prefrontal cortex, inferior parietal lobule, lateral temporal cortex, and hippocampus).

Resting-state and food-viewing stimulated neural activity will be measured in younger adults only.

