The major potential risks in this study are related to the sleep restriction, blood draw, and the MRI/fMRI. 1. Risks associated with SR: Participants may feel sleepy and irritable during the SR phase. They may feel drowsy, less attentive, or have difficult concentrating. 2. Risks associated with blood drawing: At the baseline visit and weeks 3, 4, 5, and 6, routine venipuncture will be performed for screening laboratory studies, and on the oral glucose tolerance test days, an antecubital vein catheter will be inserted in one arm for multiple blood sampling. Drawing blood and inserting an intravenous line into an arm vein are safe and standard medical procedures. Sometimes a bruise will occur at the puncture site and rarely a blood clot or infection will occur in the vein. Certain individuals may feel light-headed during venipuncture. The volume of blood collected during this study will be no more than 30 mL per time point. This is not expected to have any serious negative effects on a study participant. 3. Risks associated with MRI and fMRI scanning: There are no significant risks associated with the use of MRI except the risk of flying object in the magnetic field. MRI scanning involves the use of a magnet and radio frequency waves (much like an ordinary short-wave radio). - There are no known risks or adverse effects resulting directly from exposure to magnetic fields and radio frequency signals used in this study, other than the potential risks associated with the scanning procedure summarized below. - MRI uses a strong magnetic field to create images of the body. Because of the strong magnetic field, the greatest risk is that a metal object could be pulled into the scanner and hit someone. - Some people may feel confined and experience anxiety in the scanner. - The scanner produces tapping sounds during operation, which may reach very loud levels. - In extremely rare cases, a magnet can lose its magnetism, in which case cooling fluids may be released noisily through escape valves and may collect in gas form in the scan room. The gas is not harmful in itself as long as fresh air is available. - Some subjects may experience muscle twitches or tingling sensation and/or a slight increase in body temperature during some types of scan activity. These are very unlikely under current guidelines.

---

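### The listed fMRI preprocessing has no nuisance regression for the resting-state data, and the plan gives no use for the pulse, respiration, wakefulness and sleepiness data and no resting-state model

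*Combined protocol and SAP*

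**What the plan says.** Procedures, Image analysis, gives the pipeline as a list: "Preprocessing will comprise (1) slice time correction, (2) 3-D motion correction, (3) spatial smoothing (FWHM=6 mm), (4) mean-based intensity normalization", followed by "5) temporal band-pass filtering (restingstate data only; 0.009-0.1 Hz), and (6) linear and quadratic detrending". Registration to the structural image and to a standard template comes next. On motion, the section adds "we anticipate implementing 'scrubbing' to salvage offending segments with excessive motion, if necessary" and states no threshold. FSL and C-PAC are named without a configuration.

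The section on resting-state and food-viewing neural activity says what is collected during scanning: "Pulse and respiration rates will be measured using MRIcompatible non-invasive physiological monitoring equipment" and "Wakefulness and compliance with eyes-open instructions will be monitored via an eye-tracking camera and verbal reminders given before every run". Overview of Procedures adds, for the fMRI visit, "They will fill out a visual analog scale and the Stanford Sleepiness Scale, before and after the scan". No section says how any of these measurements enters the fMRI analysis.

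The only group comparison described for fMRI is a paired t-test on the food versus non-food task contrast. Hypothesis 2b, in Statistical Procedures and in Research Question(s)/Hypothesis(es), predicts stronger reward-network connectivity at rest and reduced default-mode network (DMN) synchrony after SR. No model is attached to that prediction.

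Potential Risks says of participants in the SR phase: "They may feel drowsy, less attentive, or have difficult concentrating".

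**The concern.** Resting connectivity is a correlation between regional time series. Any signal that several regions share for non-neural reasons, such as head motion or cardiac and respiratory fluctuation, adds to that correlation. The usual protection is to regress such signals out, and the listed pipeline has no step that does so.

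The crossover removes nuisance that is stable within a person. It does not remove nuisance that changes with the treatment. The plan itself warns that SR may make participants drowsy, and each phase's scan falls in its last week. Motion and breathing can therefore differ between SR and HS scans of the same person. If shared nuisance is higher under SR, the paired contrast shows a rise in connectivity with no change in reward circuitry. That is the direction Hypothesis 2b predicts for the reward networks, so an artefact could be read as confirmation.

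**Working it through.** **1. Text check.** The plan states no sample size, power or significance level for resting connectivity, so there is no figure of its own to reproduce. The pieces side by side:

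| Item | Collected or planned | Stated use in the resting-state analysis |
|---|---|---|
| Head motion | Restraint pads, 3-D motion correction, conditional scrubbing | No regression of motion parameters; no scrubbing threshold |
| White-matter and CSF signal | Available from the images | None |
| Pulse and respiration rates | Measured | None |
| Wakefulness | Monitored by camera, with reminders | No exclusion rule, no covariate |
| Stanford Sleepiness Scale | Before and after the scan | None |
| Group model | Paired t-test for the task contrast | None for resting connectivity |

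**2. Can the band-pass filter do the job?** Input from Image analysis: TR = 2.5 s.
- Sampling frequency = 1/2.5 = 0.40 Hz; Nyquist frequency = 0.20 Hz.
- Alias frequency = distance from the true frequency to the nearest multiple of 0.40 Hz.
- Breathing at 20/min = 0.333 Hz, which appears at 0.400 - 0.333 = 0.067 Hz.
- Pulse at 75/min = 1.25 Hz, which appears at 1.25 - 1.20 = 0.05 Hz.
- Both lie inside the 0.009-0.1 Hz pass-band.

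The documents give no rates, so I assumed ranges. About 25% of a 12-20/min respiration range and about 37% of a 50-90/min pulse range fold into the pass-band. The filter cannot be relied on to remove physiological signal.

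**3. Illustration of size. All of these inputs are assumed.** True correlation r = 0.30 in both phases; SR adds a shared nuisance share f relative to HS. Observed correlation = r + f(1 - r). Fisher z of 0.30 is 0.3095.

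| f | Observed r | Fisher z | Shift in z |
|---|---|---|---|
| 0 | 0.300 | 0.3095 | 0 |
| 0.03 | 0.321 | 0.3328 | 0.023 |
| 0.05 | 0.335 | 0.3484 | 0.039 |
| 0.10 | 0.370 | 0.3884 | 0.079 |

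For a paired t-test with the 50 completers planned in Statistical Procedures, the noncentrality is shift/SD × √50. With f = 0.05 and an assumed paired SD of 0.20 it is 0.0389/0.20 × 7.071 = 1.38. A two-sided 0.05 test then rejects in the predicted direction 27% of the time, against a nominal 2.5%. Across f = 0.03-0.10 and SD 0.15-0.25 the rate runs from 9% (f = 0.03, SD 0.25) to 95% (f = 0.10, SD 0.15). The width of that range shows how little the documents fix.

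**4. Direction for the DMN.** Because f(1 - r) is positive for every r below 1, the same mechanism raises DMN correlations too. It opposes the predicted fall in DMN synchrony.

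**5. Cost in data.** Two runs of about 5 min at 2.5 s give 300/2.5 = 120 volumes per run, 240 in all. Each nuisance regressor is paid for out of that.

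**The case against.** Several points on the other side stand.

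- **The description may be incomplete rather than the pipeline deficient.** The list covers task and rest together. A task heading has no resting-state counterpart, and a bracket opened just before it is not closed, so source text may have been abridged. A grant application is listed among the attachments but is not available here. The claim is therefore about what is stated. The list is nevertheless worded as complete, and no other section adds the step.
- **Motion is not ignored.** Besides realignment and restraint pads, the plan reports pilot mean head motion of 0.073-0.078 mm against a field standard of 0.2 mm. This is reassuring on motion, but it is not broken down by sleep condition and says nothing about cardiac or respiratory signal.
- **The bias has no anchor in the documents.** The correlation, nuisance share and SD are all assumed, and equal shares give no bias.
- **Drowsiness caused by SR is part of what SR does.** It affects whether a difference is read as reward valuation or as vigilance; it does not invalidate the randomized contrast. Regressing pulse and respiration would not remove it, and adjusting the main contrast for it would condition on a consequence of treatment.

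A reader might also infer that cardiac, respiratory and eye-closure series are on file and only need to be entered in the model. The text does not support that: it speaks of measuring rates and monitoring wakefulness, and nowhere says that waveforms or eye-tracking series are stored.

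**Conclusion.** The concern holds in a limited form. As written, the plan has no nuisance regression for resting-state data, gives no analytic role to the physiological, wakefulness and sleepiness measurements, and specifies no resting-state model. Treatment-related nuisance would survive the paired comparison and could imitate the reward-network half of Hypothesis 2b.

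The 0.023-0.079 shift in Fisher z rests on an assumed true r of 0.30 and an extra shared share of 0.03-0.10 under SR. It illustrates the mechanism and is not an estimate for this trial.

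Two stronger readings are tempting and not supported. The first is that artefact could account for all of Hypothesis 2b: extra shared signal raises DMN correlations, and nothing in the documents says that drowsiness lowers DMN synchrony. The second is that an error rate can be quoted for the 36 participants reported as completing. That count is not restricted to the younger adults, who alone have fMRI, and the number of them with two usable scans is not given.

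The impact is confined to the resting-state part of Hypothesis 2b in younger adults. Adiposity, energy intake and the sample size are untouched.

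**What to change.** For the resting-state data, specify before the analysis is run:

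1. Regression of motion parameters with their derivatives, and of white-matter and CSF signals, done before or jointly with band-pass filtering. Add cardiac and respiratory regressors only if waveforms were stored.
2. A fixed motion threshold for scrubbing, applied identically to both phases, in place of the conditional wording.
3. The subject-level connectivity measure and the group model. The main result is the paired SR-HS contrast without adjustment for sleepiness.
4. Motion, pulse and respiration rates, and sleepiness scores reported by phase.
5. A motion- and sleepiness-adjusted contrast as a sensitivity analysis only, labelled as such because these variables may be consequences of SR.

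The study is at the data-analysis stage and C-PAC is already named, so items 1 and 2 mean rerunning preprocessing without new participants. The cost is fewer degrees of freedom from about 120 volumes per run, and fewer still where volumes are censored.
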